The CDC's initial interim guidelines for dental settings during COVID-19 suggested that using a pre-procedural rinse with an antimicrobial product (such as chlorhexidine gluconate, essential oils, hydrogen peroxide, povidone-iodine, or cetylpyridinium chloride) could have a potential effect in reducing the level of oral microorganisms in aerosols and spatter generated during dental procedures⁷. In April 2020, the CDC and the American Dental Association (ADA) recommended using a mouthwash containing 1.0-1.5% H₂O₂ as a pre-procedural rinse before dental treatment to reduce SARS-CoV-2 load potentially; however, no US clinical studies have been conducted to support this claim.

This study aims to assess the effect of four over-the-counter (OTC) antiseptic mouthwash/gargling solutions compared to a distilled water control on the SARS-CoV-2 load in unstimulated saliva, throat wash (gargle lavage), and oropharyngeal swab samples. Also, study participants will be assessed for the severity of their clinical symptoms during the study period. The 4-week protocol was selected as studies show people with COVID can continue to shed the virus and potentially transmit to the others for a 2- to 4-week period. This study will also examine tobacco use, marijuana smoking, or vaping as possible effect modifiers of antiseptic mouthwash on SARS-CoV-2. Study participants will be followed up daily via a very short daily questionnaire and every 3 months for the next 11 months after the study is finished for longerterm follow-up via text messaging. The null hypothesis of the study is that there is no difference between any OTC antiseptic mouthwash solution (Chlorine Dioxide (ClO₂), Hydrogen Peroxide (H₂O₂), Cetylprydinium Chloride (CPC), Essential Oils (EO), and distilled water (H₂O) in reducing SARS-CoV-2 load in unstimulated saliva, throat wash (gargle lavage), and oropharyngeal swab samples (baseline to 4 week follow-up).

Objectives {7}

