1a. To assess and compare the SARS-CoV-2 viral load in unstimulated saliva and throat wash (gargle lavage) samples before and after rinse at baseline in Chlorine Dioxide (ClO₂), Hydrogen Peroxide (H₂O₂), Cetylprydinium Chloride (CPC), and Essential Oils (EO) groups versus distilled water (H₂O) group (pre-procedural rinse primary outcome measure).1b. To assess the SARS-CoV-2 viral load reduction of throat wash (gargle lavage) samples from baseline to 4 weeks in Chlorine Dioxide (ClO₂), Hydrogen Peroxide (H₂O₂), Cetylprydinium Chloride (CPC), and Essential Oils (EO) groups versus distilled water (H₂O) group solution of throat wash (gargle lavage) samples from baseline to 4 weeks in Chlorine Dioxide (ClO₂), Hydrogen Peroxide (H₂O₂), Cetylprydinium Chloride (CPC), and Essential Oils (EO) groups versus distilled water (H₂O) group (homecare reduction primary outcome measure).

2. To assess the clinical symptom onset progression and health care utilization (e.g. hospitalization) from baseline to 4 weeks comparing Chlorine Dioxide (ClO₂), Hydrogen Peroxide (H₂O₂), Cetylprydinium Chloride (CPC), Essential Oils (EO) to distilled water (secondary outcome measures).

3. To assess if tobacco use, marijuana smoking, or vaping are effect modifiers of primary outcome measures.

4. To evaluate study participants' in a 12-month follow up.

Trial design {8}

This is a single center, 5-arm, parallel groups, double-blinded (participant, outcomes assessor),

randomized controlled trial of adults who are COVID-19 positive using over-the-counter (OTC) mouthwash/gargling solutions: Chlorine Dioxide (ClO₂) (CloSYS Ultra Sensitive, Rowpar Pharmaceutical Inc., USA); Hydrogen Peroxide (H₂O₂) (Oral-B Mouth Sore, Proctor & Gamble, USA); Cetylprydinium Chloride (CPC) (Crest Pro-Health Multi-Protection, Proctor & Gamble, USA); Essential Oils (EO) (Listerine Zero, Johnson & Johnson, USA) versus distilled water as a control.

Methods: Participants, interventions and outcomes

Study setting {9}

Consenting community-dwelling San Francisco Bay Area (California, USA) participants positive for COVID-19.

Eligibility criteria {10}

Inclusion criteria

- Adults 18 years and older
- Tested positive for COVID-19 with a sample collected in the prior 7 days
- Ability to read and speak in English or Spanish
- Ability to participate in the study for 4 weeks
- Ability to gargle
- Not having any oral condition that might worsen with gargling solutions

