The study participants should not use any other mouthwashes or take any antimicrobial medication (antibacterial, antiviral, antibiotics including off-label usage such as Remdesivir) during the study. They can continue practicing their usual home oral hygiene care (tooth brushing with a toothpaste, and flossing). If they have a dental emergency (e.g. dental infection such as abscess or pulp infection) they should contact their regular dentist for dental treatments according to their dentist's COVID protocols.

Provisions for post-trial care {30}

The antiseptic mouthwash solutions to be used by study participants are safe over-the-counter solutions that are available without requiring dentist's prescriptions, to improve oral health conditions. Unless individuals might be allergic to the ingredients of the study mouthwashes, they will not face any harm and risks when using the solutions. However, research team will provide their phone numbers and emails if participants confront any problems during the study period. If study participants feel any stress and discomfort due to their COVID-19 status, they will be advised to contact their physician and COVID-19 hotlines as soon as possible to receive required health services. After the study is finished, participants will be asked a few questions by texting a link to an online questionnaire designed in REDCap in about every 3 months over the

next 11 months to see how they are doing, their clinical symptoms, acceptability of using the assigned mouthwash during the trial, and their potential use after the trial.

Outcomes {12}

Primary outcome Measure:

- Change in SARS-Cov-2 viral load: Change in RT-PCR SARS-Cov-2 viral load in unstimulated saliva and throat wash (gargle lavage) samples (Time Frame: Baseline to 4 weeks)

Secondary Outcomes Measures:

- Change in self-reported (questionnaire) clinical symptom onset. A symptom checklist will include: cough, runny nose, scratchy/sore throat, fever, chills, fatigue, muscle ache, shortness of breath, diarrhea/nausea/vomiting, loss of taste/smell, and red /painful eye (Time Frame: Baseline to 4 weeks)
- Change in healthcare utilization and hospitalization (Time Frame: Baseline to 4 weeks) Other Pre-specified Outcome Measures:
 - Change in SARS-Cov-2 viral load in tobacco users, marijuana smokers, or vapers (Time Frame: Baseline to 4 weeks)

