At any time during the trial, if a participant discontinues from the study or deviates from intervention protocols, we will record the information.

Data management {19}

We have planned to use unique barcodes on sample collection kits and participants' packages to be scanned during the trial and automatically recorded in an Excel file on a UCSF secured laptop and the Cloud. Only PIs know about the codes. [name] (SB) will supervise data entry and its quality on a regular basis. Data will be linked to a REDCap form.

Confidentiality {27}

Email address and telephone number are the only personal identifying information which will be kept confidential in REDCap on UCSF secured servers. Participant information will be kept confidential. After the study and its follow-up in 12 months is finished, email address and phone number will be deleted.

Plans for collection, laboratory evaluation and storage of biological specimens for genetic or molecular analysis in this trial/future use {33}

The study procedures include collecting saliva and oropharyngeal samples from participants on 3 study days (day 1, 7, 28), assaying them, and storing them for future potential research use.

Statistical methods

Statistical methods for primary and secondary outcomes {20a}

Primary outcome measure: To assess and compare the SARS-CoV-2 viral load in unstimulated saliva and throat wash (gargle lavage) samples at baseline, days 7 and 28, we will compare the viral load (cycle threshold, Ct) among active groups versus the control (water) and within groups on day 28 using proportional hazards regression models with right censoring for undetermined Ct, stratifying on replicate for a marginal repeated measures survival model.

We follow the intention-to-treat (ITT) approach for efficacy analyzing participant data asrandomized; a safety analysis will tabulate any adverse experiences. The ITT group will include participants who are randomized after meeting the eligibility criteria and receive at least one study mouthwash dose and have PCR data from collected samples. A safety analysis group will include participants who received study mouthwashes and have safety evaluation data after using the mouthwash at least once.

Interim analyses {21b}

We plan to conduct an interim analysis after 10 participants in each group (N=50) have finished the 28-day period (using mouthwash). The alpha-spending approach with an O'Brien-Fleming stopping rule will be used.

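### The primary outcome is change in viral load from baseline, but the active-versus-water models name no baseline Ct covariate; adding it is a cheap, lower-priority gain in power, not the repair of an error

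*Combined protocol and SAP*

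**What the plan says.** - Outcomes {12} defines the primary outcome as "Change in RT-PCR SARS-Cov-2 viral load in unstimulated saliva and throat wash (gargle lavage) samples (Time Frame: Baseline to 4 weeks").
- Objectives {7}, 1b, is "To assess the SARS-CoV-2 viral load reduction of throat wash (gargle lavage) samples from baseline to 4 weeks", each active group against water. Objective 1a concerns "samples before and after rinse at baseline" and is labelled the "pre-procedural rinse primary outcome measure".
- Section {20a} gives the model: "we will compare the viral load (cycle threshold, Ct) among active groups versus the control (water) and within groups on day 28". It is a proportional hazards regression with undetermined Ct right-censored, "stratifying on replicate for a marginal repeated measures survival model". No covariate is named.
- Section {20b} applies similar models after the rinse and at day 7, again without naming a covariate. It also says that results will be related to baseline variables, and gives demographics, symptoms and tobacco use as examples.
- Section {20c} allows multiple imputation of Ct above the detection level as an alternative. It names no covariate either.
- The Abstract has baseline specimens taken before the assigned rinse is used, and section {33} has samples from days 1, 7 and 28 assayed.

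**The concern.** The outcome is defined relative to baseline, but the between-arm model works on follow-up Ct alone. The pre-rinse value is already collected for each participant and is likely to predict the later value to some degree. Leaving it out gives up power in a trial with 24 evaluable participants per arm, which section {14} says can detect only a rather large effect. It also leaves a chance difference in starting viral load in the treatment contrast, since randomisation is stratified on language only ({16a}). Objective 1a has most to gain: its before and after samples come from the same visit, so their correlation may be high. A covariate left unnamed may also end up being chosen after the data are seen.

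**Working it through.** **1. The plan's own figures.** Enrolment reproduces: 24 / 0.80 = 30 per arm, and 5 × 30 = 150. The 80% power cannot be checked directly because no SD is stated. Back-solving a two-sample t-test (24 per arm, two-sided 0.05, 80% power) gives a standardised difference d = 0.826. Check: noncentrality = 0.826 × √(24/2) = 2.86 on 46 df, power 80%.

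**2. Linear approximation.** Adjusting for baseline multiplies the residual variance by (1 − rho²), so the effective difference is d/√(1 − rho²). A raw change score has variance 2(1 − rho), so its effective difference is d/√(2(1 − rho)).

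| rho | d/√(1 − rho²) | power, covariate | power, raw change |
|---|---|---|---|
| 0.3 | 0.866 | 83.5% | 65.8% |
| 0.5 | 0.954 | 89.9% | 80.0% |
| 0.7 | 1.157 | 97.5% | 95.1% |

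Follow-up alone gives 80%. A change score is therefore worse than follow-up alone below rho 0.5, while the covariate loses essentially nothing at any rho.

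**3. The planned type of model.** This was simulated because a Cox model on censored Ct behaves differently from a t-test. Assumptions: normal Ct, one Ct per person, 24 per arm, d = 0.826, 30% Spanish speakers, and a permutation test within language on null-model martingale residuals (4,000 runs per cell). The censored share is that of the water arm. Power without and with baseline Ct:

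| Controls undetermined at day 28 | rho 0.3 | rho 0.5 | rho 0.7 |
|---|---|---|---|
| none | 72% / 74% | 72% / 80% | 70% / 92% |
| 50% | 61% / 62% | 60% / 66% | 60% / 77% |
| 70% | 46% / 47% | 44% / 50% | 45% / 59% |

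Type I error was 4.2% to 5.8%. With two replicates per person (assumed intraclass correlation 0.9) and 10% of baselines undetermined, the rho 0.5 figures were 74.5% / 83.3%, 66.4% / 72.0% and 52.2% / 56.8%.

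**4. How heavy day-28 censoring could be.** Entry requires "Tested positive for COVID-19 with a sample collected in the prior 7 days", and the background puts shedding at "people with COVID can continue to shed the virus and potentially transmit to the others for a 2- to 4-week period". Day 28 can therefore fall about 4 to 5 weeks after the qualifying sample. With 70% of controls undetermined, the assumed effect leaves about 91% of the active arm undetermined. Expected detections are then 24 × 0.30 = 7.2 against about 2.1.

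**5. Objective 1a.** The after-rinse sample is taken at the baseline visit, so 28-day attrition does not apply and about 30 per arm is the right number. With 20% of controls and 10% of baselines undetermined, power rises from about 80% to 87% at rho 0.5, and from about 80% to 95% at rho 0.7. Using 24 per arm would give 72% to 81% and 70% to 90%.

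**6. Chance imbalance.** The SD of a baseline mean difference is √(2/24) = 0.289 SD. A difference above 0.4 SD has probability 2(1 − Φ(0.4/0.289)) = 0.166. On the uncensored scale it carries 0.4 × rho into the contrast: 0.12, 0.20 and 0.28 SD at rho 0.3, 0.5 and 0.7.

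**7. Side effects.** At rho 0.5 uncensored, the median log hazard ratio (SE) moves from −0.80 (0.31) to −0.97 (0.32). The interval does not narrow, and the power comes from a larger conditional effect. Ordinary or robust Wald tests on the adjusted model reached type I error of 8.4% (day 28), 8.6% (with replicates) and 9.4% (objective 1a). Entering an undetermined baseline at the limit plus an indicator failed to converge in 15% to 78% of runs at 50% censoring; without the indicator, failures were at most 0.1%.

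**8. Interim look.** A Lan-DeMets O'Brien-Fleming spend, 2(1 − Φ(1.96/√t)), is 0.0007 at t = 10/30 and 0.0024 at t = 10/24. With 499 permutations the smallest p-value is 1/500 = 0.002, too coarse. With 10,000 it is about 0.0001.

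**The case against.** The strongest reply is that nothing here is wrong. Randomisation makes the unadjusted comparison valid. On a linear scale the expected between-arm difference in follow-up equals that in change, so a reader who infers that the plan tests the wrong quantity, or that its result is biased, goes beyond the documents. This stands.

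It is also fair that the plan is silent on covariates and does not exclude them. The list of baseline variables in {20b} is open-ended, and the within-group comparison may use baseline. But that sentence sits under additional analyses, does not list Ct and does not adjust the treatment contrast. A within-arm comparison does not adjust it either, and {20a} does not say what is compared within groups.

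Third, section {14} puts precise effect estimates ahead of power, and adjustment does not narrow the interval for the log hazard ratio. This stands too: the gain serves testing and correction of imbalance, not that aim.

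Finally, day 28 may benefit least. With 70% of controls undetermined the gain is 6 points at rho 0.5 and 1 point at rho 0.3. A reader might hope that adjustment rescues a heavily censored day-28 comparison, but it does not. These points lower the priority without removing the gain.

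**Conclusion.** The point holds as a cheap improvement of lower priority. No between-arm model names the pre-rinse Ct, although the outcome is a change and the specimens are assayed. At 24 per arm and rho 0.5, the covariate is worth about 8 points of day-28 power with no censoring and about 6 points with 50% or 70% of controls undetermined. At rho 0.3 it is worth about 0 to 2 points. For objective 1a, at about 30 per arm, it is worth about 7 points at rho 0.5 and 15 at rho 0.7. All of this rests on the back-solved 0.826 SD effect, normally distributed Ct, and assumed rho and censoring shares that the documents do not give. Rho 0.5 is not a threshold: the gain grows steadily with rho and shrinks with censoring.

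**What to change.** In {20a} and {20b}, add the same specimen's pre-rinse baseline Ct as a covariate in each active-versus-water model. Apply the same rule under the multiple-imputation alternative in {20c}. Never use the after-rinse value, which follows treatment.

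- **Undetermined baseline:** enter it at the assay limit, without a separate indicator.
- **Missing baseline:** fill it by a simple rule blind to arm, for example the overall mean, so that no randomised participant is dropped.
- **Test:** use one that is valid in small samples. An example is a permutation test on the score statistic (null-model martingale residuals) that re-randomises whole persons, with all their replicates, between the two compared arms within language. Use at least 10,000 permutations so that the interim O'Brien-Fleming boundary can be reached.
- **Reporting:** give the unadjusted analysis as a sensitivity analysis and do not use a raw change score. State what is compared within groups, and treat it as supportive only.

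The cost is no new data but somewhat more programming, including a convergence check. The hazard ratio becomes conditional on baseline, and its log-scale interval is no narrower. If an ordinary Wald test were used instead, type I error could rise to about 9%.

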 - Change in self-reported (questionnaire) clinical symptom onset in tobacco users, marijuana smokers, or vapers. A symptom checklist will include: cough, runny nose, scratchy/sore throat, fever, chills, fatigue, muscle ache, shortness of breath, diarrhea/nausea/vomiting, loss of taste/smell, and red /painful eye (Time Frame: Baseline to 4 weeks)
 - Change in healthcare utilization and hospitalization in tobacco users, marijuana smokers, or vapers (Time Frame: Baseline to 4 weeks)

Participant timeline {13}

Study participants will remain in the trial for 4 weeks. After completing the intervention, they will be followed up for the next 11 months via text messaging to ask about clinical symptoms and healthcare utilization, experience using mouthwash, and their interest in using mouthwash after the trial.

Sample size {14}

A total of 150 eligible individuals will be enrolled in the trial after providing informed consent and randomly assigned to 1 of 5 groups. This trial is sized to provide precise estimates of effect size for a future definitive trial with at-risk individuals. However, this trial would be able to detect a rather large effect: a sample size of 24 for a mouthwash group and 24 for the distilled water control group is estimated to have 80% power to detect a 2-fold difference in mean values between the 2 groups with a 2-sided alpha=0.05. Assuming 80% retention through 28 days, 30 participants per group at baseline (150 total) will be enrolled.

Recruitment {15}

Two recruitment routes have been planned for this trial:

1- Upon referring to testing centers at UCSF individuals will receive the trial details via a letter or flyer, and if tested positive for COVID-19, they will contact study staff and enroll into the trial.

2- The UCSF Clinical and Translational Science Institute (CTSI) Participant Recruitment Program (PRP) provides new COVID+ patient lists enabling us to contact COVID+ patient who are interested in participating in research studies.

After study staff confirm their eligibility, participants will receive the sample collection package and written instructions at their home along with scheduling a videoconference to collect saliva samples and use the assigned mouthwash during the 4-week period.

Assignment of interventions: allocation

Sequence generation {16a}

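### The plan sets no error control across four rinses or the primary specimens: at its only stated level, two-sided 0.05, a false difference would arise in about 16% (one specimen) or 21–28% (either of two) of null trials

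*Combined protocol and SAP*

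**What the plan says.** The introduction, in its last paragraph before Objectives {7}, sets a single hypothesis: "The null hypothesis of the study is that there is no difference between any OTC antiseptic mouthwash solution" and water, covering saliva, throat wash and oropharyngeal swab.

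The analysis is framed differently. In Statistical methods {20a}, "we will compare the viral load (cycle threshold, Ct) among active groups versus the control (water", at day 28, by proportional hazards regression on Ct in saliva and throat wash. Within-group comparisons are planned as well.

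Sample size {14} treats one pair, "a sample size of 24 for a mouthwash group and 24 for the distilled water control group", and claims "80% power to detect a 2-fold difference in mean values between the 2 groups with a 2-sided alpha=0.05". That is the only place in the text supplied where a significance level appears.

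The primary specimens vary by section. Outcomes {12} lists "Change in RT-PCR SARS-Cov-2 viral load in unstimulated saliva and throat wash (gargle lavage) samples". Objective 1b names throat wash alone for the 4-week primary outcome. Objective 1a adds a further primary outcome, the before/after-rinse comparison at baseline.

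The only error control is in Interim analyses {21b}: "The alpha-spending approach with an O'Brien-Fleming stopping rule will be used". The text supplied gives no global test, no adjusted contrasts, no gatekeeping and no specimen hierarchy. It also does not say that the tests are unadjusted or only descriptive.

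**The concern.** The stated null is rejected if any one rinse is declared different from water. With four contrasts, and perhaps two specimens each, there are four to eight chances to do so. All contrasts share one water arm, so an unusually high or low water result moves them together.

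Alpha spending limits the error from looking twice at one comparison. It does not limit the error from looking at several. Nor does {21b} say which comparison must cross the boundary, or whether any one of them is enough. The interim look comes at 10 completers per group, and Dissemination plans {31a} foresees a preprint of important early findings. A single nominally significant contrast could therefore be reported with a much weaker error guarantee than its p-value suggests.

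**Working it through.** **The plan's own figures.** 24 / 0.80 = 30 per group and 5 × 30 = 150, as stated. The 24 itself cannot be checked, because {14} gives no SD. On a normal approximation it implies a standardised difference of (1.960 + 0.842) × √(2/24) = 0.81. If 2-fold means one Ct (perfect doubling, an assumption), the implied SD is 1/0.81 = 1.24 Ct. Below, 24 per group and 80% power are taken as given.

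**Inputs.** Two-sided 0.05, so c = 1.960 ({14}); four rinses against one water arm of equal size ({14}, {20a}); one specimen (Objective 1b) or two ({12}, {20a}). The correlation r between specimens is not in the documents and is varied.

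**Four rinses, one specimen.** With Zᵢ = (eᵢ − e₀)/√2, any two contrasts correlate at ρ = 0.5. Under the joint null,

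P(any difference) = 1 − ∫ φ(x) [Φ((c + √ρ·x)/√(1−ρ)) − Φ((−c + √ρ·x)/√(1−ρ))]⁴ dx = 15.6%.

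Dropping the second Φ term counts favourable results only and gives 7.8%. For reference, four independent tests would give 1 − 0.95⁴ = 18.5%.

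**Four rinses, two specimens, either sufficing** (simulation, 1,000,000 replicates):

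| Assumed r | Any false difference | False favourable result |
|---|---|---|
| 0.3 | 28.0% | 14.3% |
| 0.5 | 26.9% | 13.5% |
| 0.7 | 24.8% | 12.4% |
| 0.9 | 21.3% | 10.7% |

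If the same rinse had to be significant in both specimens, the two-sided error would be 1.8% (r = 0.3) to 9.7% (r = 0.9).

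**Effect of the interim rule.** Repeating this with O'Brien-Fleming-type spending at information 10/24 or 10/30 gives about 15.5–15.7% for four tests and 21.2–28.2% for eight. The spending rule leaves the error across comparisons essentially unchanged.

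**Cost of adjustment.** The two-sided Dunnett critical value for four contrasts (normal approximation) is 2.442, a per-test level of 0.0146.

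- Noncentrality at the plan's effect: 1.960 + 0.842 = 2.802.
- Power after adjustment: Φ(2.802 − 2.442) = Φ(0.360) = 64%.
- Effect detectable with 80% power, log scale: (2.442 + 0.842)/2.802 = 1.172 times the log effect, so 2^1.172 = 2.25-fold.
- Size needed to keep 80% at 2-fold: 24 × 1.172² = 32.97, so 33 evaluable; 33/0.80 = 41.25, so 42 enrolled per arm, 210 in total.
- Bonferroni over four (0.0125), which is also Holm's first step: power 62%.

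**The case against.** The strongest reply is that this is a pilot, sized by its own account to estimate effects for a later trial, and that the rinses have different active ingredients. Whether distinct treatments sharing a control need familywise control in a pilot is debated, and a purely descriptive pilot would not need it. This lowers the severity. It does not remove the point, because the plan itself states a joint null, claims power at a stated alpha, sets a stopping rule and plans early release of findings.

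Four stronger readings are tempting, and the documents do not support them.

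- A reader might infer that 16–28% is the chance of wrongly calling a rinse effective. That range counts differences in both directions, including a rinse looking worse than water. The favourable-direction figure is about 8–14%.
- A reader might infer that the plan prescribes eight unadjusted tests at 0.05 and rules out a global test. It does not. {20a} is silent on level and adjustment, and a five-arm regression could supply a global test. The defect is that silence.
- A reader might add Objective 1a's immediate-rinse tests to the count. They are labelled primary in {7}, but the after-rinse analyses are placed under additional analyses in {20b}. They also come from the same participants, so a combined figure resting on independence would be unsupported. None is given here.
- A reader might infer that a false early stop is likely. At information 10/24 the interim two-sided level is 2(1 − Φ(1.960/√(10/24))) = 0.0024, so eight tests spend at most 8 × 0.0024 = 1.9%. Nearly all the excess error arises at the final analysis.

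**Conclusion.** The point holds at moderate severity. The plan has one joint null and several routes to rejecting it, with control only over time. If each contrast is tested at two-sided 0.05, the joint null is falsely rejected about 15.6% of the time when throat wash alone is primary, roughly three times the nominal 5%. If either of two specimens suffices, the figure is about 21–28%. A false favourable result occurs in about 8%, or 11–14%, against 2.5% for one test.

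These figures rest on four assumptions: 0.05 carries over from {14} to {20a}; the arms are equal in size; the normal approximation holds; and, for two specimens, the correlation lies between 0.3 and 0.9. Within-group, baseline and day-7 tests are not counted.

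The power figures inherit the plan's unverified 80%. {14} speaks of means, while {20a} plans a hazard model. Read as a hazard ratio of 2, 48 events would give 67% power even before adjustment.

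**What to change.** Settle the following before the look at 10 completers per group.

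1. **{7}, {12}, {20a}:** reconcile Objective 1b with the other two sections. Name one primary specimen, or one pre-specified combined analysis. A combined analysis with a single effect per rinse changes what is estimated, so the choice should be explicit.
2. **{20a}:** test the joint null once, with a 4-df test across the five arms. Report the four rinse-versus-water contrasts with Dunnett- or Holm-adjusted p-values and simultaneous intervals. State whether the 4-df test is a gate. The contrast adjustment controls the familywise error without one, and a gate would cost some power not included in the 64%.
3. **{21b}:** say that the spending boundary applies to that adjusted test.
4. **{14}:** state that, taking 24 per group and 80% as given and working on a log scale, Dunnett adjustment gives about 64% power for a 2-fold difference, or 80% power for about 2.25-fold. Give the SD that was assumed.

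The cost is wording and analysis work, plus a less favourable power statement. No extra enrolment is needed. Keeping 80% power at 2-fold with Dunnett adjustment would instead take 42 per arm, 210 in total.
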